Sample size calculations: From our pilot data, mean baseline systolic BP was 162.9 (SD 25.6). Change from baseline to 6 months with the TEAM Uganda intervention saw a mean systolic BP of 149.7 (SD 22.1). Reductions BP of ≥ 2 mm Hg can significantly reduce the incidence of cardiovascular disease and its complications in both hypertensive and normotensive individuals, and reductions of the magnitude seen in this team's pilot work is well above thresholds that are considered clinically meaningful.^{94, 95} Our projected sample size is n=246, with 123 participants per arm. Based on our preliminary mixed model, we observed difference in systolic BP from baseline to 24 weeks of 13.22, with standard deviation of 25.84, and within subject correlation parameter value of 0.57. However, we will conservatively estimate our sample size based upon a difference of 10 mmHg, commensurate with a meta-analysis that used this magnitude of change in BP across a large sample with varying baseline blood pressure levels and comorbidities.⁹⁶ Also in our pilot work with the TEAM Uganda study, we observed an attrition rate of 12.5% at 6-months follow-up. Conservatively, for this study, we will assume 25% attrition. Finally, to assume for two-sided test of time-by-treatment group interaction, Type I error level is 0.05. Then, in a linear mixed model with subject-level and center-level random effects, power is 0.80 for a clinically significant difference of 10.0 mm Hg between treatment arms for the projected sample size of 246 subjects in total. We should thus have sufficient power. We do assume compound symmetry over the 3 time periods. We will also consider an AR(1) covariance model, and compare model fits.

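### The mixed model's covariance is left open between compound symmetry and AR(1); an unstructured matrix would remove that choice, and the 0.80 power should be stated as conditional on the baseline-to-6-month correlation

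*Combined protocol and SAP*

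**What the plan says.** Under Data Analysis Plan, Sample size calculations, the plan states "Our projected sample size is n=246, with 123 participants per arm", assumes 25% attrition, and takes pilot values "with standard deviation of 25.84, and within subject correlation parameter value of 0.57". The calculation is for a "two-sided test of time-by-treatment group interaction", and "Type I error level is 0.05". In a mixed model with random effects for participant and center, "power is 0.80 for a clinically significant difference of 10.0 mm Hg between treatment arms". On covariance it says: "We do assume compound symmetry over the 3 time periods". The next sentence is: "We will also consider an AR(1) covariance model, and compare model fits". No fit criterion is given, no structure is designated for the primary test, and an unstructured matrix is not mentioned anywhere.

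The same section reports pilot systolic SDs of 25.6 at baseline and 22.1 at 6 months. Under Quantitative data Analysis, the effect of main interest is the treatment-by-time interaction from baseline to 6 months. That text assigns a 2-group by 3-wave repeated measures ANOVA to each of H1-H3, with Mauchly's test and an adjusted F if sphericity fails, and treats mixed models as something that may be explored. However, the Secondary outcomes paragraph refers to a primary mixed model, and the Missing Data paragraph rests its validity argument on the mixed model.

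**The concern.** The standard error of a baseline-to-6-month contrast depends on the variances at those two visits and the correlation between them. Compound symmetry and homogeneous AR(1) each have two parameters. Neither lets that correlation be estimated separately from the other visit pairs, and neither lets the variances differ, although the pilot variances differ by a ratio of (25.6/22.1)² = 1.34. A poorly fitting structure can therefore make the primary standard error too small or too large. Leaving the choice open also makes the primary p-value depend on a decision taken after the outcome data are seen. Finally, the power of 0.80 is stated without saying which visit pair its correlation describes, so a reader cannot tell how far it would fall if correlation weakens over time.

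**Working it through.** **Inputs** (Sample size calculations): 123 per arm, 25% attrition, two-sided 0.05, difference 10 mmHg, SD 25.84, correlation 0.57, pilot SDs 25.6 and 22.1. The plan does not say whether 25.84 is the SD of BP or of its change, or which visits 0.57 refers to.

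**Step 1: reproduce the stated power.** Completers per arm: 123 × 0.75 = 92.25, taken as 92. With 25.84 as the SD of BP, SD of change = 25.84 × √(2 × (1 − 0.57)) = 23.96. SE = 23.96 × √(2/92) = 3.53, and 10/3.53 = 2.83. Two-sample t-test power is 0.804, matching 0.80. Taking 25.84 as the SD of change gives SE 3.81 and power 0.74, which does not match. So the stated figure is consistent with 0.57 acting as the baseline-to-6-month correlation, as it does under compound symmetry.

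**Step 2: power against that correlation r.** Equal-SD column: SD of change = 25.84 × √(2(1 − r)). Pilot-SD column: √(25.6² + 22.1² − 2r × 25.6 × 22.1). Both use 92 per arm.

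| r, baseline to 6 months | SD of change (equal SDs) | Power | SD of change (pilot SDs) | Power |
|---|---|---|---|---|
| 0.57 | 23.96 | 0.80 | 22.33 | 0.86 |
| 0.45 | 27.10 | 0.70 | 25.19 | 0.76 |
| 0.325 | 30.03 | 0.61 | 27.86 | 0.68 |

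The value 0.325 is 0.57² and arises only if 0.57 is the adjacent-visit correlation under AR(1). If 0.57 is instead an average over the three visit pairs with AR(1) decay, (2a + a²)/3 = 0.57 gives a = 0.646 and a² = 0.418, with power 0.68 at equal SDs.

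**Step 3: cost of the wrong structure (closed form, complete data).** Compound symmetry pools the three correlations. If AR(1) with adjacent correlation 0.57 is true, the pooled value is (0.57 + 0.57 + 0.325)/3 = 0.488. The SE is then √((1 − 0.488)/(1 − 0.325)) = 0.871 of its proper size, and type I error is 2 × (1 − Φ(1.96 × 0.871)) = 0.088. With adjacent correlation 0.57 and baseline-to-6-month correlation 0.45 or 0.40, the same formula gives 0.070 or 0.078.

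Conversely, AR(1) with 0.57 when compound symmetry holds inflates the SE by √((1 − 0.325)/(1 − 0.57)) = 1.253. Type I error is 2 × (1 − Φ(2.456)) = 0.014 and power is Φ(2.83 − 2.456) = 0.65.

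**Step 4: simulation.** There were 2,000 trials per setting with REML fits. Dropout was assumed completely at random: 12.5% before week 13 and 25% by month 6. For the pilot-SD row a week-13 SD of 23.85 (the midpoint) was assumed. Type I error by fitted structure:

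| True structure | Compound symmetry | AR(1) | Chosen by AIC | Unstructured |
|---|---|---|---|---|
| Compound symmetry, 0.57 | 0.049 | 0.018 | 0.048 | 0.052 |
| AR(1), adjacent 0.57 | 0.086 | 0.048 | 0.050 | 0.048 |
| Adjacent 0.65, baseline-to-6-month 0.45 | 0.082 | 0.040 | 0.040 | 0.042 |
| AR(1), baseline-to-6-month 0.57 | 0.091 | 0.046 | 0.046 | 0.046 |
| Pilot SDs, correlation 0.57 | 0.038 | 0.012 | 0.038 | 0.042 |

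Simulation error at 0.05 is √(0.05 × 0.95/2000) = 0.005. Power when compound symmetry (0.57) is true: 0.823 with compound symmetry, 0.686 with AR(1), 0.826 unstructured. When AR(1) with adjacent 0.57 is true: 0.656 with AR(1), 0.653 unstructured.

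Simulations with 92 complete participants per arm agree: about 0.07-0.09 for compound symmetry under decay, 0.012-0.014 for AR(1) when compound symmetry holds (power 0.66), and 0.044-0.063 when chosen by fit. In one complete-data setting with baseline-to-6-month correlation 0.45, fit selected compound symmetry 51% of the time, yet type I error was 0.055.

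**The case against.** The strongest reply is that the analysis text names repeated measures ANOVA for H1. Its linear contrast over three waves weights the visits −1, 0, 1, which is exactly baseline versus 6 months. Tested against its own error term, that contrast needs neither compound symmetry nor AR(1): simulated type I error under AR(1) was 0.051 with 92 completers per arm. This stands. The covariance choice matters only if the mixed model is primary, and the plan points both ways. Settling that comes first.

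Three stronger readings are tempting and are not supported.

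- *The primary test will have the wrong error rate.* The rates of 0.09 and 0.012 belong to keeping one structure when it is wrong. The plan says it will compare fits, and choosing by fit gave about 0.04-0.06. Even selection by fit is an inference: the wording fits a sensitivity comparison equally well.
- *True power is 0.61.* The 0.80 needs a baseline-to-6-month correlation near 0.57, not compound symmetry as such. If 0.57 already describes that pair, power is about 0.80 under AR(1) too. The plan reports 0.57 in the same sentence as the baseline-to-24-week difference, which favors that reading without settling it. Using the pilot SDs raises power at every correlation shown.
- *An unstructured matrix is always free and protects power.* It showed no measurable loss here, but it uses six parameters instead of two and does not bring back 0.80 if correlation decays (0.653 in the simulation).

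**Conclusion.** The point holds as an inexpensive improvement. The plan leaves the mixed model's covariance open between two restrictive structures. Retaining the wrong one would give type I error of about 0.07-0.09 (compound symmetry under decay) or a conservative test with power of about 0.66-0.69 (AR(1) when compound symmetry holds). An unstructured matrix stayed between 0.042 and 0.053 in every setting tried. Because choice by fit also stays near nominal on average, the benefit is robustness and the removal of a post-hoc decision. The unequal pilot SDs do little harm to type I error by themselves (0.038 with compound symmetry in that row).

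The stated power is reproduced, but it is conditional on a baseline-to-6-month correlation near 0.57. These results assume about 92 completers per arm, dropout completely at random where it was simulated, normal outcomes and no center effect.

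**What to change.** In the Data Analysis Plan:

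1. State that the mixed model described under Sample size calculations, rather than the repeated measures ANOVA, carries the primary test of H1 through the baseline-to-6-month treatment contrast.
2. Pre-specify an unstructured covariance over the three visits with Kenward-Roger degrees of freedom, retaining the center effect.
3. If that model does not converge, fall back to a less restrictive structure such as heterogeneous Toeplitz, or to robust standard errors. Plain compound symmetry should not be the fallback, since it brings back the structure at issue.
4. Report compound symmetry and AR(1) as sensitivity analyses.
5. State which visits the 0.57 describes, and give power as conditional on the baseline-to-6-month correlation: 0.80 at 0.57, 0.70 at 0.45, and 0.61 at 0.325 (SD 25.84, 92 completers per arm). Note that the last value applies only if 0.57 is the adjacent-visit correlation under AR(1).

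The cost is a few sentences, with no added participants or data. The power statement becomes conditional and somewhat less favorable.

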Quantitative data Analysis: Preliminary descriptive analyses will examine change over time in systolic BP as well as secondary outcomes. The measures of interest are valid and reliable, and have been used in stroke studies in the SSA setting.^{24, 30, 88, 97, 98} Primary and secondary outcome measurements will be assessed at baseline prior to randomization to either TEAM or ETAU, and at the 13 week and 6 month time-points using the same methods as in our pilot work. Of primary interest is the treatment by time interaction in systolic BP, measured from baseline to 6 months after randomization between TEAM and ETAU. Explanatory variables will include age, gender, stroke history and rural vs. urban status.

The 13-week systolic BP measurement will reflect the period following baseline (when individuals participating in TEAM Uganda will have just completed the “intensive” group sessions), and it will be used to assess for within-subject differences from baseline to 13 weeks and 13 week to 6-month time periods. This will allow for a greater understanding of the time course for when the expected reductions occur in the TEAM Uganda group, which we expect to mostly occur after the “intensive” group sessions have ended. We will analyze change from baseline to 13 weeks as well, analyzing contrasts within the mixed model framework.

For aim 2, we will use 2 group by 3 time waves repeated measures analysis of variance (RMANOVA) for each of the 3 hypotheses in Aims 2. These analyses will compare two groups (TEAM intervention vs. enhanced treatment as usual (ETAU)) across three time waves of systolic BP (H1), serum cholesterol (H2), and serum HbA1c (H3). When using a repeated measures ANOVA, it not only assesses mean differences across time, but also assesses group differences, as well as, the interaction of time X group which will allow us to test the trend of the means over time across the three groups. The repeated measures ANOVA, not only can be used to determine if there are mean differences across the three time periods, it can also utilize orthogonal polynomial contrasts to determine linear and quadratic trends of the means across time. Orthogonal polynomials are weights

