Missing Data: Strategies to minimize loss to follow-up are outlined in Form E, specifically the description of our Recruitment and Retention Plan. Data that remain missing despite our retention efforts will be accommodated in our analyses and their impact evaluated through sensitivity analyses. The models we propose can be estimated without bias under the missing at random (MAR) assumption¹⁰² and provide valid analysis as long as covariates associated with missingness (if any) are included in the mixed model. To assess which covariates may be associated with missing outcome data, we will create binary indicators of whether the outcome was missing (=1) or not (=0). If a covariate is correlated with missingness at $r > 0.40$ and is correlated at $r > 0.40$ with the original response variable, it will be included in the analysis as an auxiliary correlate.¹⁰³ We will conduct assessment of the missing at random (MAR) assumption by pattern mixture models that relax the missing at random assumption, while analyzing the sensitivity of treatment by time interaction effects. . We will also consider using Full Information Maximum Likelihood models in presence of incomplete data.¹⁰⁴

Qualitative data analysis plan: PIs at each of the proposed study sites will be responsible for overseeing data input and quality

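### The r > 0.40 double cut-off for auxiliary covariates is far narrower than the plan's own missing-data condition, so that condition is not assured for covariates outside the named set

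*Combined protocol and SAP*

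**What the plan says.** The Missing Data section of the Data Analysis Plan states that, under missing at random, the models "provide valid analysis as long as covariates associated with missingness (if any) are included in the mixed model". That condition sets no minimum strength of association. To find such covariates, the plan builds a 1/0 indicator of a missing outcome and applies a two-part rule: correlation above 0.40 with the indicator, and correlation above 0.40 "with the original response variable, it will be included in the analysis as an auxiliary correlate". It gives no reason for 0.40 and does not say that the correlations are taken within arm.

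Some covariates do not depend on this rule. Under Quantitative data Analysis: "Explanatory variables will include age, gender, stroke history and rural vs. urban status". The Secondary outcomes paragraph places these variables in the primary mixed model, and Sample size calculations adds a center-level random effect. The Missing Data section also commits to "pattern mixture models that relax the missing at random assumption" and adds: "We will also consider using Full Information Maximum Likelihood models in presence of incomplete data".

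**The concern.** The condition and the rule that is meant to satisfy it do not match. A covariate can be clearly associated with missingness, so that the validity sentence requires it, and still be kept out by the rule.

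The variables exposed are those collected but not on the named list. Diabetes is a balancing factor under RCT Treatment randomization, yet it is not among the explanatory variables. The Charlson index, medication access and medication adherence are also collected and not named. For missing-data purposes, all of these can enter only through the gate.

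Dropout that differs by arm is plausible. TEAM asks for an orientation and six group sessions, while ETAU is one visit and nine phone calls. Only arm-specific dropout of this kind would bias the treatment-by-time contrast, and a pooled correlation is poorly placed to detect it.

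**Working it through.** **Inputs.** From Sample size calculations: 246 participants (123 per arm), 25% planned and 12.5% pilot attrition, SD 25.84 mmHg, within-subject correlation 0.57, target difference 10 mmHg, two-sided alpha 0.05, power 0.80. From Missing Data: both 0.40 cut-offs.

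**1. The plan's own figure.** Change-score SD = 25.84 × √(2 × (1 − 0.57)) = 23.96. Completers per arm = 123 × 0.75 ≈ 92. Power = Φ(10 / (23.96 × √(2/92)) − 1.96) = Φ(0.87) = 0.81. The stated 0.80 reproduces, which supports reading 25.84 as the SD at a single time point. The 0.40 cut-offs have no derivation to reproduce.

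**2. What r = 0.40 with missingness requires.** With a proportion p missing, the gap between dropouts and completers in within-group SDs is r / [√(p(1 − p)) × √(1 − r²)].
- p = 0.25: 0.40 / (0.433 × 0.917) = 1.01 SD.
- p = 0.125: 0.40 / (0.331 × 0.917) = 1.32 SD.
- Binary covariate with 50% prevalence, p = 0.25: missingness of 42% in one category against 8% in the other.
- The same covariate at p = 0.125: the largest possible correlation is √(0.125/0.875) = 0.378, so it cannot pass.

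At n = 246, a correlation of about 0.125 is already significant at 0.05. Values from about 0.13 to 0.40 are therefore detectable associations that the rule excludes.

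**3. How often both limbs pass.** Using Fisher's z with n = 246 for missingness and n = 184 (75% of 246) for the outcome, and treating the limbs as independent, take a true r of 0.30 on both. The missingness limb gives (0.4236 − 0.3095) × √243 = 1.78, probability 0.038. The outcome limb gives 0.1141 × √181 = 1.54, probability 0.062. The product is about 0.2%. The same calculation gives about 4% at 0.35, 25% at 0.40 and 66% at 0.45.

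**4. Pooling over arms.** With equal dropout rates and a covariate balanced by randomization, the pooled correlation is about the mean of the two arm correlations. Values of +0.39 and −0.39 pool to 0. Values of 0.39 and 0 pool to about 0.20. For a normal covariate at 25% missing the largest possible correlation is 0.73, so one that acts in one arm only pools to at most about 0.37 and is expected to fail.

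**5. Bias in the 6-month arm difference.** Take a covariate with r = 0.39 on both limbs at 25% missing. Its shift in one arm's completer mean is r₁ × r₂ × √(p/(1 − p)) × SD = 0.39 × 0.39 × 0.577 × 25.84 = 2.3 mmHg. The bias in the contrast when the covariate is left out was obtained by large-sample simulation, with absolute values in mmHg and Monte Carlo error of about 0.05:

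| Link to dropout | No SBP history used | Baseline SBP used | Baseline and 13-week SBP used |
|---|---|---|---|
| Same in both arms | about 0 | about 0 | about 0 |
| One arm only | 2.2 | 0.9–1.0 | 0.6 |
| Opposite directions | 4.5 | 1.9–2.0 | 1.2–1.3 |

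With r = 0.30 on both limbs, the last column falls to about 0.4 (one arm) and 0.7 (opposite). Putting the covariate in the model removes the bias in every case.

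**The case against.** A reader might infer that the missing-at-random condition fails outright. The documents do not support that. Age, gender, stroke history, rural/urban status and a center effect are in the model without any screen. Baseline and 13-week systolic BP are responses, so a likelihood-based model uses them. The validity sentence itself allows that there may be no such covariates, and pattern mixture analyses of the treatment-by-time effect are planned. This stands: the 0.40 rule governs additional covariates only. But pattern mixture models are sensitivity analyses and do not repair the primary model's covariate set, and full-information likelihood is only to be considered.

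A reader might also infer that the rule almost never passes anything. The documents give no covariate correlations, and at true values of 0.45 the rule passes about two times in three. Step 3 shows only that it rarely passes moderate predictors.

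The largest figures are equally tempting. The 2.3 mmHg shift belongs to one arm's mean and cancels from the contrast when dropout acts alike in both arms. The 4.5 mmHg figure needs opposite links and an analysis that ignores systolic BP history. A complete-case change score would show about 0 if the covariate's link to systolic BP is constant over time.

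Two features of the rule are not faults in themselves. Requiring a link to the outcome as well as to missingness is reasonable, because a covariate unrelated to the outcome causes no bias. The absence of an absolute-value sign matters only on a very literal reading, since the sign of r depends on coding.

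**Conclusion.** The point holds in limited form. The entry rule is much stricter than the condition that it is meant to satisfy, and it is not specified within arm. The condition is therefore not assured for collected covariates outside the named set. It cannot be said to be breached.

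For a covariate just under both cut-offs, the likely cost to the 6-month contrast runs from about 0 to about 1.3 mmHg, or up to 13% of the 10 mmHg target. That is below the 2 mmHg reduction that the plan treats as meaningful. If only baseline systolic BP is available for dropouts, the upper end is about 2 mmHg.

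These sizes assume that 25.84 is the SD at each visit, that dropout is 25% in both arms, that missingness and outcome are independent given the covariate, and that the covariate's link to systolic BP is constant over time. The correlations are illustrative. The sizes also assume a likelihood-based mixed model, while Quantitative data Analysis says "we will use 2 group by 3 time waves repeated measures analysis of variance (RMANOVA) for each of the 3 hypotheses". That inconsistency is a separate matter, but it decides whether the systolic BP history is used as assumed here. The sample size is unaffected.

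**What to change.** Delete the r > 0.40 gate and state a prespecified set that is included whatever the observed correlations:
- baseline and 13-week systolic BP as responses;
- diabetes and prior stroke, as randomization factors;
- site, age, gender and rural/urban status;
- a short named list of collected baseline predictors of dropout, such as the Charlson index and medication access.

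State that any link between these variables and dropout that may differ by arm will be examined within arm.

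Do not replace the gate with a low data-driven screen. With 123 per arm and 92 observed, a rule of |r| ≥ 0.10 with either missingness or outcome in either arm makes four checks. Pure noise passes at least one with probability 1 − 0.728² × 0.656² ≈ 77%, where 0.728 and 0.656 are the chances of staying below 0.10 at n = 123 and n = 92.

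The cost is a change of wording and a few degrees of freedom in a trial of 246. The variables are already planned for collection, and of the fixed set only diabetes and the short list are new to the model.
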